2.1 Trial Design

SAHaRA is a multicenter pragmatic randomized trial in patients with aSAH that compares the effect of a liberal to a restrictive RBC transfusion strategy on the combined rate of death and severe disability at 12 months. Our PROBE (prospective, open-label, blinded endpoint) approach has been informed by and tested in our CIHR/CBS-funded pilot RCT.¹⁴

Trial interventions

Eligible patients are randomized to either a restrictive or a liberal RBC transfusion strategy. Hemoglobin is checked at least daily while on protocol up to and including Day 10 post aSAH or while in an ICU/HAU (high-acuity unit), and then at the discretion of the primary clinical team.

Restrictive RBC Transfusion Strategy: For patients randomized to this group, an RBC transfusion is permitted once a hemoglobin level of ≤ 80 g/L is observed over the first 21 days following aSAH. RBC transfusion below the threshold is not mandatory, rather “usual care” prevails, with the decision and timing of transfusion left to the discretion of the treating team.

Liberal RBC Transfusion Strategy: An RBC transfusion is triggered by a hemoglobin level of ≤ 100 g/L over the first 21 days in hospital following aSAH. Transfusion in this arm is mandatory.

Both Groups: All RBC transfusion orders are single unit unless the patient has active blood loss associated with hemodynamic instability (see section 9.1 of the protocol – see Appendix). In stable non-bleeding patients, a second unit of RBCs is given if a measured post-transfusion hemoglobin level remains below the patient’s assigned threshold. Protocol adherence and violations are discussed in section 9.1 of the protocol (see Appendix).

Duration of the intervention

The allocated transfusion strategy is applied from the time of randomization to 21 days after the original bleed, death or hospital discharge, whichever comes first. The first 21 days following aSAH represent the period of greatest vulnerability to the direct consequences of aSAH, and the sequelae, including DCI, that follow.

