3.2 Adherence and protocol deviations

The study adherence is measured in 2 domains:

1) Adherence to allocated transfusion threshold: This occurred if an RBC transfusion is given only in response to the transfusion threshold being crossed with the last hemoglobin measure prior to transfusion being below the appropriate threshold. *Non-adherence* will be considered to have occurred if a) an RBC transfusion occurs before a transfusion threshold is crossed; or b) in the liberal arm, a transfusion is not given following a threshold crossing. Non-adherence will be

considered a *deviation* if: 1) the early transfusion occurs within 5 g/L above the allocated threshold (e.g., ≤ 105 g/L for the liberal arm or ≤ 85 g/L for the restrictive arm) or, 2) in the liberal arm, an RBC transfusion does not occur for a hemoglobin measure up to 5 g/L below the threshold (i.e.: a transfusion does not occur for a hemoglobin of 95-100 g/L). All other threshold event non-adherences will be considered a protocol violation. Details on non-adherence (date and hemoglobin level prior to transfusion) and reasons for non-adherence will be recorded. In the event of an active blood loss associated with hemodynamic instability, as defined by the treating team, standard resuscitation practices prevail (including blood product administration). Transfusion under this circumstance would not be a protocol violation. The allocated transfusion strategy will resume when hemodynamic stability is achieved and it is the opinion of the treating team that active bleeding has stopped. Transfusion outside of hemoglobin thresholds for symptomatic anemia (as assessed by the bedside team) will be recorded, but not considered a protocol violation.

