3.3 Analysis populations

Intention to Treat population: this population includes all aSAH patients randomized except those who were a post-randomization exclusion, withdrew consent, or were lost to follow up.

Per Protocol Population: this population is the intention to treat population except those who had a protocol violation (as defined in 3.2).

The primary analysis of all outcomes will be conducted on the Intention to Treat population. A secondary, sensitivity analysis, on the Per Protocol population will also be conducted and reported separately, accompanied by a description of the population characteristics, in the supplement.

Section 4 – Trial Population

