4.1 Eligibility

Inclusion Criteria:

1. Age ≥ 18 years old at time of SAH

2. First ever episode of aneurysmal SAH
3. Diagnosis of aSAH as confirmed by treating physician (e.g., neurosurgeon or neuro-interventionalist) and supported by blood in subarachnoid space (e.g., cranial imaging or CSF positive for xanthochromia, surgical visualization) that is the result of a ruptured aneurysm (e.g., direct visualization, cranial imaging or catheter angiogram)
4. Hb \leq 100g/L within 10 days following aSAH (defined by first day of hospital presentation)

Exclusion Criteria:

1. Physician and or family decision to withdraw/withhold active medical care at time of enrolment.
2. Active bleeding with hemodynamic instability at time of enrolment.
3. Patients with contraindication or known objection to blood transfusions.
4. SAH due to mycotic aneurysm, infundibulum and vascular malformations.

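### In the per-protocol set, a liberal-arm patient left untransfused after care is withdrawn is dropped as a violator, while the same restrictive-arm patient is kept

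*SAP*

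**What the plan says.** The rule comes from several places read together.

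- **Obligation (SAP 2.1).** For the restrictive arm, "RBC transfusion below the threshold is not mandatory". For the liberal arm, "Transfusion in this arm is mandatory".
- **Non-adherence (SAP 3.2, domain 1; also Protocol 9.1).** Leaving a patient untransfused is listed for one arm: "in the liberal arm, a transfusion is not given following a threshold crossing". It is only a deviation when "a transfusion does not occur for a hemoglobin of 95-100 g/L". Otherwise the default applies: "All other threshold event non-adherences will be considered a protocol violation".
- **Exceptions (SAP 3.2).** There are two: bleeding with hemodynamic instability, and symptomatic anemia. Both excuse giving blood. Neither excuses withholding it.
- **Duration (SAP 2.1, Protocol 6.5).** The strategy is "applied from the time of randomization to 21 days after the original bleed, death or hospital discharge, whichever comes first". Withdrawal of care is not listed as an end point.
- **Eligibility (SAP 4.1, Protocol 6.2).** Withdrawal of care appears only as an exclusion: "Physician and or family decision to withdraw/withhold active medical care at time of enrolment".
- **Per-protocol set (SAP 3.3).** Its definition is: "this population is the intention to treat population except those who had a protocol violation (as defined in 3.2"). One violation is enough.
- **Use (SAP 3.3, 5.2).** The per-protocol analysis is one of four sensitivity analyses of the primary outcome and is reported in the supplement. The primary analysis is intention to treat.

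**The concern.** Take two patients who are alike except for allocation. Each is moved to comfort care on day 6, has a measured Hb of 92 g/L, is not transfused and dies. In the liberal arm this is an omission below 95 g/L, so the patient is a violator and leaves the per-protocol set. In the restrictive arm it is no violation at 92 g/L, nor would it be at 78 g/L, because transfusion there is discretionary. That death stays in.

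The exclusion is therefore specific to one arm and tied to prognosis. Death is mRS 6 and counts as the primary event (mRS 4 or higher, SAP 5.1). Taken alone, this route lowers the liberal arm's event rate for reasons unrelated to treatment, in the direction of the trial hypothesis (Protocol 5.1). A sensitivity analysis that shifts towards the hypothesis by construction is a poor check on the primary result.

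**Working it through.** **Does another rule balance this route?** Domain 2 of SAP 3.2 names no arm, but its violation is a transfusion started more than 24 hours after the threshold event. A patient who is never transfused cannot meet it. Early transfusion (more than 5 g/L above the threshold) can be a violation in either arm, but it too requires a transfusion. For the untransfused patient the asymmetry stands.

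**Planning figures (SAP 2.3, 2.2, 3.1).** 40% versus 30%, two-sided 5%, 80% power, 3% loss, 1:1 allocation.

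n per arm = [1.96·√(2·0.35·0.65) + 0.8416·√(0.40·0.60 + 0.30·0.70)]² / 0.10² = 356, or 712 in total. Dividing by 0.97 gives 735, close to the stated 740. (With a continuity correction it would be 776; nothing here depends on the choice.) The 740 leaves 740 × 0.97 / 2 ≈ 359 evaluable patients per arm.

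**Size of the route.** Let w be the share of the liberal arm removed by this route, all assumed to be mRS 6, and v the share of restrictive-arm deaths removed by other violations. Neither document gives w or v.

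Per-protocol rate, liberal = (p_L − w)/(1 − w); restrictive = (p_R − v)/(1 − v).

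No true effect (p_L = p_R = 40%), v = 0:

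| w | Liberal patients removed (of 359) | Liberal rate | RR | Chance the 95% interval favours liberal |
|---|---|---|---|---|
| 0 | 0 | 40.0% | 1.00 | 2.5% |
| 1% | 3.6 | 39/99 = 39.4% | 0.985 | 3.6% |
| 2% | 7.2 | 38/98 = 38.8% | 0.97 | 5.2% |
| 5% | 18.0 | 35/95 = 36.8% | 0.92 | 13.5% |

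The last column uses an unadjusted pooled two-proportion z-test, which approximates the planned log-binomial mixed model.

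Under the design effect (30% versus 40%), w = 2% moves the RR from 0.75 to (28/98)/0.40 = 0.714, and w = 5% moves it to (25/95)/0.40 = 0.658.

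**With restrictive-arm removals (no true effect).**

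- w = 5%, v = 2%: 36.8/38.8 = 0.95 (7.6% chance of favouring liberal).
- w = 5%, v = 5%: 1.00.
- w = 2%, v = 5%: 38.8/36.8 = 1.05, now against liberal.

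The direction of this one route is known. The net direction of the whole per-protocol analysis is not.

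**The case against.** A reader might infer that the per-protocol analysis removes deaths from the liberal arm alone and so must favour it. The documents do not support that. Restrictive-arm patients can also be excluded, for early transfusion or for transfusion more than 24 hours after the threshold event, and some of them may die.

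The route also has conditions. An Hb must have been measured, and SAP 2.1 requires daily checks only while the patient is on protocol, to Day 10 or in a high-acuity unit. The value must be below 95 g/L. Protocol 6.9 lets the investigator remove a participant, and neither document says whether a removed patient still accrues violations. These points limit w. They do not abolish the route, because no text says that withdrawal of care takes a patient off protocol.

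It is also tempting to say that a liberal-arm patient who dies soon after a crossing is always a violator. That is one reading of a rule with no deadline. Domain 2 allows 24 hours before a violation, and the strategy ends at death.

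Nor does the cited 35% mortality (Protocol 5) support a large w. Overall mortality is not the share dying untransfused, below 95 g/L, after withdrawal. At w = 10% the RR would be 0.83, but then a quarter of all poor liberal outcomes (10 of 40 points) would have to follow this one path. The pilot's 3 violations over 97 transfusion episodes (Protocol 5.3) are not split by arm or reason and cannot fix w.

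Finally, the analysis is supplementary, and SAP 3.1 reports a p-value only for the primary outcome. That limits the consequence but does not justify leaving the rule as it is.

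**Conclusion.** The point holds as a defect in how the per-protocol population is defined. As written, withdrawal of care followed by no transfusion removes liberal-arm patients with an Hb below 95 g/L and leaves their restrictive-arm counterparts in. Through this route the RR is pulled towards the liberal strategy: 0.985, 0.97 and 0.92 for w = 1%, 2% and 5%. Those figures assume no true effect, 40% poor outcome in both arms, all removed patients dead, and no restrictive-arm removals. They illustrate size; they do not estimate it.

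Two stronger conclusions do not follow: that the per-protocol result as a whole is biased towards liberal, and that the trial's main result is at risk. The first depends on restrictive-arm exclusions that the documents do not quantify. The second is wrong, since the intention-to-treat analysis, its type I error and the 740 sample size do not use these violation rules. The change is worth making because the per-protocol analysis is a named check on the primary outcome and a symmetric rule costs little.

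**What to change.** Before database lock, add to SAP 3.2, for defining the per-protocol population and for both arms:

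1. Threshold events after a documented decision to withdraw or withhold active care do not count as violations.
2. An omission is classified only once the 24-hour window used in domain 2 has elapsed with the patient alive and on protocol.
3. Whether a participant removed under Protocol 6.9 stops accruing violations from the date of removal.

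The events can be found from the dates and reasons for non-adherence that SAP 3.2 already requires, with source records where needed. Classification should be done without knowledge of the treatment comparison. It cannot be called blind to mRS, because item 2 depends on whether the patient has died.

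The cost is a few sentences and some source checking, since a withdrawal-of-care date is not among the listed data items. A few more untransfused liberal-arm patients will stay in the per-protocol set. Omissions for other reasons remain violations in the liberal arm only; the change addresses the prognosis-linked route, not every asymmetry. Patient care is unchanged.

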6.3 Trial interventions

Eligible patients will be randomized to either a restrictive or a liberal RBC transfusion strategy. Hemoglobin will be checked minimally daily while on protocol up to and including Day 10 post aSAH or while in an ICU/HAU (high-acuity unit), and then at the discretion of the primary clinical team.

Restrictive RBC Transfusion Strategy: For patients randomized to this group, an RBC transfusion is permitted once a hemoglobin level of ≤ 80 g/L is observed over the first 21 days following aSAH. RBC transfusion will not be mandatory under this threshold, rather “usual care” will prevail, with the decision and timing of transfusion left to the discretion of the treating team.

Liberal RBC Transfusion Strategy: An RBC transfusion will be triggered by a hemoglobin level of ≤ 100 g/L over the first 21 days in hospital following aSAH.

Both Groups: All RBC transfusion orders will be a single unit unless the patient has active blood loss associated with hemodynamic instability (see section 9.1). In stable non-bleeding patients, a second unit of RBCs should only be given if a measured post-transfusion hemoglobin level remains below the patient’s assigned threshold. Protocol adherence and violations are discussed in section 9.1.

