2) Adherence to transfusion protocol (timely transfusion): As in the pilot, we endeavor not to exceed 6 hours from transfusion threshold event to transfusion initiation, in keeping with revascularization time performance measures in stroke literature^{70,71}. Transfusion protocol adherence is thus defined as an RBC transfusion initiated within 6 hours of threshold crossing, or Randomization. Non-adherence will be considered to have occurred if there is a delay of more than six hours between transfusion threshold event and transfusion initiation. Transfusions occurring more than 6 hours but within 24 hours will be considered a protocol deviation. A violation is a transfusion initiated greater than 24 hours from the threshold event. We will document reasons for non-adherence in the study case report form.

To improve protocol compliance and awareness we have involved neurosurgeons, interventionalists, transfusion medicine and intensivists at each study site. We will provide on-call house staff and clinicians end-of-the-day and start-of-the-weekend reminders about the study, both for future recruitable patients and enrolled patients. Reminders in the form of stickers and flagged pages will mark enrolled patients' medical record. A list of randomized patients will be kept in the transfusion medicine lab to allow for a secondary check of protocol adherence for when RBC transfusion is ordered. We will monitor daily hemoglobin measures to ensure compliance of transfusion within 6-hour target of meeting the threshold.

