2) Adherence to transfusion protocol (timely transfusion): We endeavor not to exceed 6 hours from transfusion threshold event to transfusion initiation, in keeping with revascularization time performance measures in stroke literature.^{20,21} Transfusion protocol adherence is thus defined as an RBC transfusion initiated within 6 hours of threshold crossing, or Randomization. *Non-adherence* will be considered to have occurred if there is a delay of more than six hours between transfusion threshold event and transfusion initiation. Transfusions occurring more than 6 hours but within 24 hours will be considered a deviation. A protocol violation is a transfusion initiated greater than 24 hours from the threshold event. We documented reasons for non-adherence in the study case report form.

We will assess adherence by evaluating the number of:

- All protocol violations (per patient).
 - All transfusion threshold violations (per patient).
 - All time to transfusion violations (per patient).

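### The 24-hour timing rule names no arm, so it can drop restrictive patients from the per-protocol set for a delay their strategy permits, and it grades liberal-arm delay more harshly than omission

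*SAP*

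**What the plan says.** The two arms carry different obligations. In the liberal arm SAP 2.1 states "Transfusion in this arm is mandatory". In the restrictive arm Protocol 6.3 states "RBC transfusion will not be mandatory under this threshold", and SAP 2.1 describes usual care, "with the decision and timing of transfusion left to the discretion of the treating team".

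Adherence is then scored in two domains (SAP 3.2, Protocol 9.1):

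- **Threshold domain.** A missed transfusion is non-adherence in the liberal arm only. It is a mere deviation if "in the liberal arm, an RBC transfusion does not occur for a hemoglobin measure up to 5 g/L below the threshold", that is, at 95-100 g/L. Other threshold non-adherence is a violation.
- **Timing domain.** "Transfusions occurring more than 6 hours but within 24 hours will be considered a deviation"; beyond that, "A protocol violation is a transfusion initiated greater than 24 hours from the threshold event". Protocol 9.1 agrees: "A violation is a transfusion initiated greater than 24 hours from the threshold event". No arm is named in either document.

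SAP 3.3 defines the per-protocol set by exclusion: "this population is the intention to treat population except those who had a protocol violation". SAP 3.2 also plans per-patient counts of timing violations. SAP 5.2 lists the per-protocol analysis among four sensitivity analyses of the primary outcome, and SAP 3.3 places it in the supplement.

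**The concern.** A per-protocol set is meant to remove patients whose care departed from the assigned strategy. Read literally, this one can remove restrictive patients whose care stayed within it, because the timing limit applies to a decision that the strategy leaves open. The threshold domain separates the arms; the timing domain does not.

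Two things are at stake. First, exclusion would turn on a discretionary decision made after randomization, and its frequency can differ by arm, so the per-protocol risk ratio could move for reasons unrelated to adherence. Second, the adherence table would report restrictive-arm violations for permitted care. Separately, in the liberal arm the rule keeps a patient whose mandatory transfusion was omitted and drops one who received it late at the same hemoglobin.

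**Working it through.** **Step 1: apply the rules to four patients.** Assume the clock runs from the first qualifying hemoglobin, with no active bleeding or symptomatic anemia (the exemptions in SAP 3.2, which do not cover a discretionary delay).

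| Arm | Hemoglobin | What happens | Threshold domain | Timing domain | Per-protocol set |
|---|---|---|---|---|---|
| Restrictive | 79 g/L | transfused at 30 h | adherent | violation | dropped |
| Restrictive | 79 g/L | never transfused | not non-adherence | no transfusion to time | kept |
| Liberal | 97 g/L | transfused at 26 h | adherent (last value still at or below 100 g/L) | violation | dropped |
| Liberal | 97 g/L | never transfused | deviation | no transfusion to time | kept |

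The first row conflicts with SAP 2.1 and Protocol 6.3. The third and fourth rows reverse the order one would expect where transfusion is mandatory. That reversal is confined to 95-100 g/L, since omission below 95 g/L is itself a violation.

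**Step 2: check the clock.** Protocol 9.1 says a repeat value that no longer crosses the threshold ends the event. SAP 3.2 instead judges the last hemoglobin before transfusion. Neither says whether each new qualifying value restarts the 24 hours. Hemoglobin is checked at least daily through day 10 or while in a high-acuity unit (SAP 2.1). If every qualifying value restarts the clock, few patients would exceed 24 hours; if only the first counts, more would.

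**Step 3: how many patients?** The documents give no figure by arm. Protocol 5.3 reports that all pilot transfusions began within 11 hours of the trigger value. Taking its 97 episodes as the denominator (an assumption), 0 of 97 passed 24 hours. Exact two-sided 95% upper limit for zero events: 1 - 0.025^(1/97) = 3.7% of episodes, arms combined. If 48 or 20 of those episodes were restrictive (assumed, as the split is not given), the limits are 7.4% and 16.8%. These limits treat episodes as independent, and the pilot's clock start is not stated either.

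**Step 4: what could it do to the risk ratio?** The plan states no figure on this point. Its design rates, 40% restrictive and 30% liberal, give 356 per arm at 80% power and two-sided 5%. That is 712 in all, and 712/0.97 rounds up to 735, close to the stated 740; the rates are used here as given.

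Let f be the share of the restrictive arm removed and r their event rate, both assumed, with no liberal exclusions. The remaining restrictive risk is (0.40 - f·r)/(1 - f); the per-protocol risk ratio is 0.30 (true ratio 0.75) or 0.40 (true ratio 1.00) divided by that. With 370 × 0.97 ≈ 359 evaluable patients, 2% is about 7 and 5% about 18.

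| f | r | Remaining risk | True 0.75 reads | True 1.00 reads |
|---|---|---|---|---|
| 2% | 60% | 0.388/0.98 = 39.6% | 0.758 | 1.010 |
| 5% | 60% | 0.370/0.95 = 38.9% | 0.770 | 1.027 |
| 2% | 30% | 0.394/0.98 = 40.2% | 0.746 | 0.995 |
| 5% | 30% | 0.385/0.95 = 40.5% | 0.740 | 0.987 |

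At r = 40% nothing moves. If 5% are removed from each arm with risk raised by half (60% and 45%), the liberal risk is (0.30 - 0.0225)/0.95 = 29.2% and the ratio stays at 0.292/0.389 = 0.75.

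**The case against.** Four objections carry weight.

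- **The rule may rarely apply.** Only transfused patients can breach it, restrictive transfusion is optional, and the pilot saw nothing beyond 11 hours. This stands and limits the size. It does not reconcile the texts.
- **The bias has no known direction.** A reader might infer that late-transfused restrictive patients are the sicker ones, so that dropping them flatters the restrictive arm and masks a liberal benefit. The documents do not support this: they give no outcomes for such patients, the shift reverses if their risk is below the arm average, and timing exclusions also fall on the liberal arm, which Protocol 10.2 expects to receive more transfusions.
- **The reach is narrow.** The primary analysis and the only planned p-value (SAP 3.1) are unaffected. SAP 3.3 could be read as extending the per-protocol analysis to all outcomes, but SAP 5.2 and Table 4 list it for the primary outcome alone. This also stands.
- **Limiting timing exclusions to the liberal arm makes selection arm-dependent.** True, and it should be disclosed. But the arms have different obligations, and a per-protocol set should measure each arm against its own.

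**Conclusion.** The conflict is real and lies in both documents: restrictive-arm timing is discretionary in one section and can be breached in another, and SAP 3.3 turns a breach into exclusion. The liberal-arm grading of delay above omission at 95-100 g/L follows from the same section and does not depend on the discretion clause.

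The consequence is limited to a supplementary sensitivity analysis and the timing-violation counts. On the illustrative assumptions (2-5% of the restrictive arm removed, no liberal exclusions), a true risk ratio of 0.75 would read about 0.76-0.77 with a 60% event rate among those removed and about 0.74-0.75 with 30%. At the pilot's observed 0% nothing changes.

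It would go too far to say that compliant restrictive patients will be removed in number. The rule as written can remove them; how many depends on the undefined clock and on the arm split of late transfusions, neither of which the documents give.

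**What to change.** Amend SAP 3.2 and 3.3 before database lock, as an analysis classification only:

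1. Reconcile the timing domain (SAP 3.2, Protocol 9.1) with the discretion clause (SAP 2.1, Protocol 6.3), so that a restrictive-arm delay the clause allows is not a violation when the per-protocol set is built. Report restrictive time from threshold to transfusion descriptively.
2. Within the liberal arm, grade omission and delay at the same hemoglobin consistently, so that omission is never the milder class.
3. State when the threshold-event clock starts and whether a new qualifying value restarts it.

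None of this changes patient care or takes a view on the right transfusion timing. The cost is a few sentences; scoring the 6- and 24-hour classes already requires the times and hemoglobin values. There are two downsides: timing-violation counts will differ from the pilot's convention, and timing exclusions will apply to one arm only, which should be stated beside the per-protocol result.
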